1. INTRODUCTION

GS-US-162-0112 is an open-label, non-randomized rollover study that will provide FTC-203 study participants enrolled at two study centers in South Africa with continued access to the study drug, emtricitabine, following the completion of the FTC-203 study.

This document describes the statistical analysis methods and data presentations to be used in the summary and analysis of data for Study GS-US-162-0112.

1.1. Study Objectives

The objectives of this study are:

- To provide current FTC-203 study participants in South Africa with continued access to the study drug, emtricitabine, following completion of the FTC-203 study.
- To collect long-term safety information in subjects receiving emtricitabine in combination with other antiretroviral agents.

1.2. Study Design

1.2.1. Design Configuration

This is an open-label, non-randomized rollover protocol that will provide current FTC-203 study participants enrolled at the two study centers in South Africa with continued access to the study drug, emtricitabine, following completion of the FTC-203 study. A total of 59 subjects were enrolled in South Africa at two study centers, representing the maximum possible enrollment in this protocol.

1.2.2. Subject Population

HIV-1 infected pediatric subjects enrolled in FTC-203 at two study centers in South Africa who wish to continue to receive the study drug, emtricitabine, beyond completion of the FTC-203 study were eligible for enrollment. Subjects must have completed at least 96 weeks on the FTC-203 study and were required to complete the End-of-Study Visit for FTC-203 prior to transitioning into the rollover protocol.

1.2.3. Treatment Group

This is an open-label, single-arm study. All subjects were enrolled and treated with emtricitabine, administered in combination with other antiretroviral medications.

Emtricitabine is given as 6 mg/kg once daily (QD), up to a maximum of 200 mg QD using the capsule formulation or up to a maximum of 240 mg QD using the oral solution formulation, with both formulations administered orally. Other antiretroviral medications were administered at the dose or doses recommended by the manufacturer in the relevant product/package insert for the treatment of pediatric patients.

1.2.4. Key Eligibility Criteria

Current FTC-203 study participants were eligible to participate in this rollover protocol if

- 1) they completed all End-of-Study Visit procedures for the FTC-203 study, and
- 2) either
 - a. they had a plasma HIV-1 RNA viral load of ≤ 400 copies/mL at the End-of-Study Visit, or
 - b. if the subject's plasma HIV-1 RNA viral load was > 400 copies/mL at the End-of-Study Visit, their viral load was $< 1.0 \log_{10}$ above the nadir recorded after Week 8 of the FTC-203 study and there was reliable genotypic evidence showing a lack of resistance to emtricitabine.

1.2.5. Study Periods/Phases and Duration

Each eligible subject electing to participate in the rollover protocol continued to receive emtricitabine, in combination with other antiretroviral medications, for as long as they continued to meet the following virologic criteria:

- they have a plasma HIV-1 RNA viral load of ≤ 400 copies/mL, or
- if the subject's plasma HIV-1 RNA viral load is > 400 copies/mL, their viral load is $< 1.0 \log_{10}$ above the nadir recorded after Week 8 of the FTC-203 study and there is reliable genotypic evidence showing a lack of resistance to emtricitabine,

and until either: (1) the subject chooses to discontinue treatment of emtricitabine and withdraw from the rollover protocol; (2) the subject experiences a toxicity that necessitates the permanent discontinuation of emtricitabine, or (3) emtricitabine is approved for market distribution in the subject's country of residence.

1.2.6. Schedule of Assessments

Study procedures at screening, baseline, and during the study are outlined in the protocol and presented in Appendix 1 of the Statistical Analysis Plan (SAP).

During the rollover protocol, the Investigator will manage each subject according to current "standard of care" practices at his (or her) institution, with the subject returning to the clinic approximately every 12 weeks for study visits (i.e., four visits per year). The Investigator may choose to have the subject return to the clinic on a more frequent basis as part of their standard of care, but these visits will be outside of the protocol-defined visit schedule.

Data collection during the rollover protocol for safety purposes will be limited to the reporting of adverse events (AEs) that (1) meet the criteria for a serious adverse event (SAE), (2) result in permanent discontinuation of the study drug, emtricitabine, and/or (3) are associated with skin discoloration (hyperpigmentation). Information relating to the dispensing and accountability of the study drug will also be recorded.

Non-serious AEs that do not result in the discontinuation of emtricitabine and/or are not associated with skin discoloration (hyperpigmentation), the results of routine clinical laboratory testing (hematology, clinical chemistry and urinalysis), immunological data (absolute and percent CD4+), pregnancy test results, and physical examination findings collected in the FTC-203 study will no longer be collected or recorded in the case report form (CRF), nor will the findings of any assessments done according to current standard of care practices be recorded in the CRF.

2. GENERAL CONSIDERATIONS FOR DATA ANALYSIS

2.1. All Enrolled Analysis Set

The all enrolled analysis set includes all subjects who are enrolled into the study. This is the analysis set for all listings.

2.2. Safety Analysis Set

The safety analysis set will include all enrolled subjects who have received at least 1 dose of study drug.

2.3. Subject Grouping

Subjects will be grouped to one group: emtricitabine (FTC).

2.4. Analysis Windows

Study Day 1 is defined as the day when the first dose of study drug in this study, as recorded on the study drug accountability case report form. Baseline visit is defined as the Study Day 1 visit.

Study Day is calculated relative to Study Day 1. For events that occurred on or after Study Day 1, Study Day is calculated as (visit date minus date of the first dose plus 1). For events that occurred prior to Study Day 1, Study Day is calculated as (visit date minus date of the first dose).

Subject visits might not occur on protocol-specified days. Therefore, for the purpose of analysis, observations will be assigned to analysis windows.

The analysis windows (for height, weight, AE visits, etc) are presented in Table 2-1.

Table 2-1. Analysis Windows

	Nominal Day	Visit Window
Baseline		≤ 1
Week 12	84	[2, 126]
Week $12*k$, $k = 2, 3, \dots, 43$	$84*k$	[$84*k-41, 84*k+42$]

3. SUBJECT DISPOSITION

3.1. Subject Enrollment

A listing of enrollment, including investigator name and informed consent date will be provided. Subjects' demographic information (see Section 4) will also be included in this listing.

Subjects who do not meet the inclusion and exclusion criteria will be listed.

3.2. Disposition of Subjects

The summary of subject disposition will be provided. This summary will include the number of subjects enrolled and subjects in the safety analysis set.

In addition, the number and percentage of the subjects in the following categories will be summarized:

- Subjects completing study. These are subjects whose reasons for discontinuation are end of study, or end of rollover study;
- Subjects rolled over to Study GS-US-292-1515;
- Prematurely discontinued study (with summary of reasons for discontinuing study).

The denominator for the percentages of subjects in the above category will be the number of subjects in the safety analysis set.

A data listing of reasons for study drug discontinuation will be provided.

3.3. Study Drug Accountability

Drug accountability data along with subjects' height and weight collected on the same form will be listed.

4. DEMOGRAPHICS

Subject demographic data were not collected for this study but were collected for the FTC-203 study. These data will be obtained by linking the data in FTC-203 using subject ID. Subject demographic data collected in Study FTC-203 (age, sex, ethnic origin) will be summarized for subjects enrolled in Study GS-US-162-0112 using descriptive statistics (sample size, mean, SD, median, Q1, Q3, minimum and maximum) for continuous data and by the number and percentage of subjects for categorical data. Age is calculated as age in years at the baseline visit of this study. The summaries of demographic data will be provided for the safety analysis set.

5. EFFICACY ANALYSIS

No efficacy analyses will be performed as no efficacy endpoints were defined for this study.

6. SAFETY ANALYSIS

6.1. Special Events

Subjects with the following special events (if any) will be listed:

- Subjects with SAE
- Subjects with AE leading to study termination

The AE details (eg, reported AE term , AE start date, end date, relationship to study drug, action taken) were only collected for subjects with AE leading to study termination.

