### 7.2. Assessment of Adverse Events

AEs that (1) meet the criteria for a serious adverse event (SAE) (as defined in Section 7.3), (2) lead to permanent discontinuation of the study drug, emtricitabine, and/or (3) are associated with skin discoloration (hyperpigmentation) will be assessed by the Investigator and recorded on the appropriate CRF page, including the date of onset and resolution, severity, relationship to study drug or study procedures, emtricitabine, outcome and action taken with the study drug. No other AEs will be recorded.

Severity should be recorded and graded according to the GSI-modified DAIDS/NIAID Common Toxicity Grading Scale (see Appendices 3 and 4 to this protocol). The relationship to the study drug, emtricitabine, or study procedures should be assessed using the following definitions:

- **No:** Evidence exists that the AE has an etiology other than the study drug or study procedures (e.g., pre-existing condition, underlying disease, intercurrent illness, or concomitant medication).
- **Yes:** A temporal relationship exists between the event onset and administration of the study drug or between the event and the study procedures. It cannot be readily explained by the subject's clinical state or concomitant therapies and, in the case of the study drug, appears with some degree of certainty to be related, based on the known therapeutic and pharmacologic actions or AE profile of the study drug. In case of cessation or reduction of the dose, the event abates or resolves and reappears upon re-challenge. It should be emphasized that ineffective treatment should not be considered as causally related in the context of AE reporting.

These criteria in addition to good clinical judgment should be used as a guide for determining the causal assessment. If it is felt that the event is not related to the study drug, then an alternative explanation should be provided.

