### **Clarification of Serious Adverse Events**

- Death is an outcome of an AE, and not an AE in itself. In reports of death due to “Disease Progression”, where no other information is provided, the death will be assumed to have resulted from progression of the disease being treated with the study drug.
- All deaths, regardless of cause or relationship, must be reported for subjects on study and for deaths occurring within 30 days of last study drug dose or within 30 days of last study evaluation, whichever is longer.
- “Occurring at any dose” does not imply that the subject is receiving study drug at the time of the event. Dosing may have been given as treatment cycles or interrupted temporarily prior to the onset of the SAE, but may have contributed to the event.
- “Life-threatening” means that the subject was at immediate risk of death from the event as it occurred. This does not include an event that might have led to death, if it had occurred with greater severity.
- Complications that occur during hospitalizations are AEs. If a complication prolongs hospitalization, it is a SAE.
- “In-patient hospitalization” means the subject has been formally admitted to a hospital for medical reasons, for any length of time. This may or may not be overnight. It does not include presentation and care within an emergency department.
- The Investigator should attempt to establish a diagnosis of the event based on signs, symptoms and/or other clinical information. In such cases, the diagnosis should be documented as the AE and/or SAE and not the individual signs/symptoms.

A distinction should be drawn between serious and severe AEs. An AE that is assessed as grade 4 (potentially life-threatening) should not be confused with a SAE. Severity is a category utilized for rating the intensity of an event; and both AEs and SAEs can be assessed as grade 4.

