#### **7.4.                   Serious Adverse Event Reporting Requirements**

##### **7.4.1.               All Serious Adverse Events**

GSI has requirements for expedited reporting of SAEs meeting specific requirements to worldwide regulatory authorities; therefore, GSI must be notified immediately regarding the occurrence of any SAE that occurs after the screening (initial) visit, including SAEs resulting

from study procedures performed from screening onwards. The procedures for reporting all SAEs, regardless of causal relationship, are as follows:

- Record the SAE on the AE CRF and complete the “Serious Adverse Event Report” form.
- Fax the SAE report to the attention of the GSI Global Drug Safety Department (GDS) within 24 hours of the Investigator’s knowledge of the event. GDS contact information is provided below.
- For fatal or life-threatening events, also fax copies of hospital case reports, autopsy reports, and other documents when requested and applicable.

GSI Global Drug Safety: Name:

PPD

Manager, GDS

Telephone:

PPD

(Working Days)

Fax:

PPD

Email:

PPD

GSI Medical Monitor:

Name:

[name].

Sr. Clinical Research Physician, Clinical Research

Telephone:

PPD

(Working Days) /

Cellphone:

PPD

(Medical Emergencies)

Fax:

PPD

Email:

PPD

GSI may request additional information from the Investigator to ensure the timely completion of accurate safety reports.

The Investigator must take all therapeutic measures necessary for resolution of the SAE. Any medications necessary for treatment of the SAE must be recorded onto the concomitant medication section of the subject’s CRF.

Follow-up of AEs will continue through the last day on study (including the follow-up, off study drug period of the study), until the Investigator and/or GSI determine that the subject’s condition is stable, or up to 30 days after the last dose of study drug, whichever is longer. GSI may request that certain AEs be followed until resolution.

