## 7.8. Risks for Women of Childbearing Potential or During Pregnancy

The risks of treatment with the study drug, emtricitabine, during pregnancy have not been evaluated. Animal studies do not indicate direct or indirect harmful effects of emtricitabine with respect to pregnancy. Please refer to the latest version of the Investigator's Brochure for additional information. Barrier contraception should always be used in combination with other methods of contraception (*e.g.*, oral or other hormonal contraceptives) by females of child bearing potential who are less than 2 years post-menopausal while participating in the study and for 30 days following the last dose of study drug. Male subjects in the study who are sexually active must use barrier contraception for the same period of time with their female partners of childbearing potential or agree to abstain from heterosexual intercourse for the duration of their participation in the study.

The subject must be instructed to discontinue the study drug (and other medications, as applicable) and inform the Investigator **immediately** if she becomes pregnant during the study.

The Investigator should report all pregnancies to the GSI within 24 hours of becoming aware of the pregnancy. The Investigator should counsel the subject regarding the possible effects of prior study drug exposure on the fetus and the need to inform the study center of the outcome of the pregnancy.

Any pregnancy complication or elective termination of a pregnancy for medical reasons will be recorded as an SAE. A spontaneous abortion is always considered to be an SAE and will be reported as described in the AE and SAE sections. Furthermore, any SAE occurring as an adverse pregnancy outcome post-study must be reported to GSI.

Additionally all pregnancies that occur during the study should be reported using the Pregnancy Report CRF page. Monitoring of the subject should continue until the conclusion of the pregnancy. The outcome should be reported to GSI using the Pregnancy Outcome (and Abnormal Pregnancy Outcome, if applicable) CRF page(s). If the end of the pregnancy occurs after the study has been complete, the outcome should be reported directly to GSI. Pregnancies that occur after the subject has discontinued study drugs do not require monitoring.

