## **8. STATISTICAL CONSIDERATIONS**

No statistical analyses are planned. Data listings will be generated for all data collected in the clinical database. Listings will include subject enrollment/disposition, demographics (from the FTC-203 clinical database), SAEs, AEs leading to permanent discontinuation of study drug, emtricitabine, AEs associated with skin discoloration (hyperpigmentation), and study drug dispensing/accountability. Tabular summaries will be prepared.

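### SAP 6.1 plans an SAE listing but says AE details were collected only for subjects with an AE leading to study termination, and gives neither a reason nor another source for the remaining SAEs

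*SAP*

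**What the plan says.** SAP 6.1 plans two listings: subjects with an SAE, and subjects with an AE leading to study termination. It then gives examples of AE details (reported term, start and end dates, relationship to study drug, action taken) and says they "were only collected for subjects with AE leading to study termination".

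Protocol 7.2 puts three kinds of AE in scope: serious events, events leading to permanent discontinuation of emtricitabine, and events associated with hyperpigmentation. All three are to be "recorded on the appropriate CRF page, including the date of onset and resolution, severity, relationship to study drug or study procedures", with outcome and action taken named in the same sentence. Protocol 7.4.1 covers all SAEs whatever their cause. Its first instruction begins "Record the SAE on the AE CRF and complete the" and goes on to name the SAE report form, which must reach the sponsor's drug safety department within 24 hours.

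Protocol 8 plans listings of everything in the clinical database and names SAEs separately from AEs leading to permanent discontinuation. SAP 1.2.6 and SAP Appendix 1, footnote 7, still include serious AEs among the events recorded in the CRF.

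**The concern.** The SAE listing is the only SAE output in the SAP, and SAP 1.1 gives long-term safety information as one of two objectives. No efficacy analysis is planned (SAP 5). If details exist only for subjects whose AE ended their participation, the listing can identify the other subjects with an SAE but cannot say what happened, when, or whether the investigator thought it related to emtricitabine. A reader could not then judge those events from the study's own output.

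The SAP deals with a similar gap elsewhere. Section 4 says that demographics were not collected in this study, names FTC-203 as the source and gives the linking key. Section 6.1 has no equivalent for SAEs.

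**Working it through.** No arithmetic applies: the plan states no SAE count, and the point depends on no sample size or error rate. The check is a comparison of texts.

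**Step 1. What is required against what SAP 6.1 says was collected.**

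| Item | Protocol 7.2 and 7.4.1, every SAE | SAP 6.1, subject with an AE leading to termination | SAP 6.1, SAE subject without such an AE |
|---|---|---|---|
| The event itself | On the AE CRF | Collected | Not collected |
| Onset and end dates | Required | Collected | Not collected |
| Relationship | Required | Collected | Not collected |
| Action taken | Required | Collected | Not collected |
| Severity, outcome | Required | Not named (the SAP list is by example) | Not named |
| Separate SAE report form | Required | Not mentioned | Not mentioned |

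The last column is the gap. The SAP sentence is worded by subject, so it is also unclear whether a non-terminating SAE is covered in someone who later stopped because of a different AE.

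**Step 2. Does the rest of the SAP resolve it?** SAP 1.2.6 and footnote 7 keep serious AEs within CRF recording but specify no fields. They show that SAE recording was not dropped, but the field-by-field conflict is with the protocol. SAP 6.2 covers hyperpigmentation through its own assessment data and is not a source of SAE details. No section mentions the SAE report form or a safety database.

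**Step 3. Can an SAE fall in the last column?** Yes. Protocol 7.3 makes in-patient hospitalization an SAE without requiring that drug be stopped, and Protocol 7.6 permits treatment interruptions, so a subject can have an SAE and remain in the study.

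SAEs after a stop for some other reason are a second route, but a weaker one:

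- Protocol 7.3 requires reporting of "deaths occurring within 30 days of last study drug dose or within 30 days of last study evaluation, whichever is longer". It also treats death as the outcome of an AE, and that AE may itself have caused the termination, in which case its details were collected.
- Protocol 7.8 says "A spontaneous abortion is always considered to be an SAE", and Protocol 6.4 lists pregnancy as a stopping reason apart from toxicity. Pregnancy outcome CRF pages may hold some of this information, although the SAP plans no listing of them.

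**Step 4. Is there another source?** If Protocol 7.4.1 was followed, an SAE report form exists for every SAE. The documents do not show how complete those forms are.

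**The case against.** The strongest reply is that the sentence is a disclosure, not a choice. It is in the past tense, a SAP cannot create fields that were never captured, and readers are told that details will be missing. Protocol 8 confines listings to the clinical database, and 6.1 keeps to that. This stands in part: the documents do not settle whether the gap arose in data capture or in drafting. The missing reason and the missing source remain, and both are within the SAP's control.

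A second reply is that the SAP follows a later protocol. There is evidence for this. SAP 3.2 has a disposition category "Subjects rolled over to Study GS-US-292-1515", a study that the supplied protocol never mentions. SAP Appendix 1 adds HIV-1 RNA at the baseline, 12-weekly and discontinuation visits and rewrites the height and weight footnote, compared with Protocol Appendix 2. A later version could have narrowed AE recording, but the SAP cites no such change.

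Three stronger readings are tempting, and the documents do not support them.

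- A reader might infer that SAE details were never collected, or that expedited reporting failed. SAP 6.1 says nothing about the report forms sent to the sponsor, so neither follows.
- A reader might use the analysis windows to measure how much timing is lost, since SAP 2.4 says "The analysis windows (for height, weight, AE visits, etc) are presented in Table 2-1". Those windows assign visits and do not bound onset. With visits on Days 84 and 168, an SAE on Day 100 reported at Day 168 falls in the Week 24 window (168 − 41 = 127 to 168 + 42 = 210), although Day 100 itself lies in the Week 12 window (2 to 126).
- A reader might say that Protocol 8 obliges the SAP to tabulate SAEs. It says "Tabular summaries will be prepared" without naming any table, so an SAE count is optional.

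**Conclusion.** The point holds and should be fixed. Followed as written, SAP 6.1 lists an SAE that did not lead to termination with no event, dates or relatedness, contrary to what Protocol 7.2 and 7.4.1 require as supplied and with no stated reason or alternative source.

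Its size cannot be given as a number: the documents report no SAE count, and the number affected may be zero. Confidence is high in the mismatch and in the absence of a named source. It does not extend to any claim that the sites failed to collect the data. The conclusion assumes that the supplied protocol's AE recording rules apply; if a later version changed them, the remaining defect is that the SAP does not say so.

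One related wording is also open. SAP 6.1 speaks of study termination, where Protocol 8 speaks of permanent discontinuation of study drug. No section equates the two, so they should not be assumed to mean the same thing.

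**What to change.** Amend SAP 6.1 as follows.

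1. For each SAE, take term, onset, resolution, severity, relationship, outcome and action taken from the SAE report forms or sponsor safety records that Protocol 7.4.1 calls for. Reconcile them with the clinical database, list them, and mark the source of each row.
2. Where no report is found, list the subject and declare the limitation.
3. State which protocol version the SAP follows and why collection departs from Protocol 7.2 and 7.4.1, and say how study termination relates to permanent discontinuation of study drug.

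Optionally, add the number and percentage of safety-set subjects with at least one SAE, which needs no event details.

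The cost is some SAP wording, one reconciliation and a fuller listing. Nothing further is asked of subjects. Because the completeness of the SAE reports is not known, some rows may stay incomplete and carry the declared limitation.
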